We believe TXA has the potential to assist in perioperative control of hemorrhage during burn excision surgery leading to decreased blood loss and smaller transfusion rates. These potential improvements in care may translate into decreased surgical complications and a potential reduction in hospital stay and overall costs.

5. Setting of the Research:

Spectrum Health Butterworth Campus

6. Resources Available to Conduct this Research:

The Spectrum Health Regional Burn Center admits nearly 120 patients each year. Many of these patients require surgical management of their sustained injuries. Study personnel will

include attending burn surgeons and surgical residents with experience in surgical research and knowledge of surgical outcome measures. In addition, the Spectrum Health Office of Clinical Research Operations (OCRO) staff will assist with the informed consent process and subject enrollment, data collection and management, Institutional Review Board (IRB) communication and continuing renewal submission, ongoing subject management, and maintenance of the regulatory files and essential documentation for the study.

7. Study Design:

a. Recruitment Methods

Potential subjects will be recruited during the preoperative period for a planned procedure with any of the burn attending surgeons. A member of the Spectrum Health OCRO will obtain informed consent. This will take place in a private consultation room to ensure privacy and should take approximately 45-60 minutes. In order to minimize coercion, it will be made very clear to patients that their participation is strictly voluntary and that choosing not to participate will in no way affect their care at Spectrum Health.

Study Subjects

Potential subjects include all patients scheduled to undergo burn excision surgery with a deep partial or full thickness burn wound area of at least 350 cm² that meet all of the inclusion criteria, and none of the exclusion criteria. For a procedure to be included within the study, 96 hours must have elapsed since the previous procedure in which the patient was randomized to drug or placebo. If the patient has undergone a procedure outside the scope of this study, the 96-hour waiting period does not apply.

i. Inclusion Criteria

- Subjects undergoing burn excision surgery for standard of care purposes (to include: greater than or equal to 350 cm² of full thickness or deep partial thickness burns)
- Male or female \geq 18 years of age

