The study design will be a randomized, double-blinded, placebo-controlled trial, with the randomization to occur on a per procedure basis. Following satisfaction of inclusion/exclusion criteria and enrollment into the study by the Spectrum Health OCRO research staff, the subject and each procedure the patient undergoes will be assigned a study number. A single consent will be obtained for randomization of each procedure that a patient may undergo meeting inclusion criteria for the study. A single study participant could potentially be randomized to both treatments of the study if that participant undergoes two or more procedures. Each procedure a participating subject undergoes will be randomized based on a predetermined randomization schedule, created by an independent statistician at Grand Rapids Medical Education Partners (GRMEP) research department. The randomization schedule will be held by the pharmacists and checked prior to each procedure to determine the appropriate treatment (placebo or TXA). Surgical timing will be coordinated with the OCRO. The study participants will receive preoperative intravenous TXA or Normosol as placebo treatment. The preparation will be indistinguishable by nursing, surgical, or anesthesia staff. The TXA procedures will receive a 1000 mg dose immediately preceding surgical incision administered by the anesthesia provider, while the placebo procedures will receive an equivalent volume of Normosol. The dose will be administered via intravenous piggyback over 15 minutes. Operative details will be recorded including procedure performed, IV fluids received, estimated blood loss, lowest recorded body temperature, and transfused blood products. Perioperative hemoglobin level data will also be collected. Standard daily laboratory measurements will continue unless clinical conditions necessitate more frequent monitoring, per standard practice. Transfusion will take place for hemoglobin levels < 7.0 g/dL or hemoglobin level < 10 g/dL with clinical symptoms indicating need for transfusion, per standard practice. Final decision on transfusion will be made according to the staff surgeon's discretion.

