It is anticipated that each patient will receive an average of three major surgical procedures during the treatment of their burn injury. The number of procedures may range from a single procedure to greater than 6 procedures for an individual patient depending on the extent of their injury. The time between subsequent procedures typically ranges from ten days to several weeks. Prior to each procedure, the patient will be re-randomized to receive TXA or placebo.

Data to be recorded includes patient demographics (age, sex, height, weight), burn injury characteristics (total body surface area, location, depth of burn), hospital admission date, hospital discharge date, past medical history, past surgical history, medications, and laboratory values. Data from operative records will include procedure date, procedure performed, wound measurements, lowest body temperature, operative blood loss, operative time, amount of fluid received, and intraoperative transfusion requirements. Postoperative data to be collected includes hemoglobin and hematocrit levels, transfusion requirements, surgical complications, skin graft survival (%), thromboembolic events, and length of hospital stay.

d. Data Management

The Spectrum Health OCRO research staff will collect outcome data at the time of each surgical procedure. Data will be stored in a password-protected REDCap

database. The OCRO will also keep a secure record of the procedures randomized to the TXA and placebo arms, which will be blinded from the study personnel.

e. Provisions to Monitor the Data for the Safety of Subjects

Adverse events including infections, allergic reactions, graft loss, respiratory failure, anaphylaxis, thromboembolic events and development of acute renal failure will be monitored and recorded at the time of occurrence by the Spectrum Health OCRO research staff. In the event an increased number of unanticipated events occur, the study will be temporarily stopped pending review. A review of unblinded data will be performed by an independent clinician and statistician at Grand Rapids Medical Education Partners to determine the need to discontinue or resume the study. If a significant increase in adverse events is noted in the treatment arm related to the study drug, the trial will be terminated. Decisions resulting from the review will be discussed with the primary investigator.

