Interim reviews of unblinded data for statistically significant findings will be performed by an independent clinician, pharmacist, and statistician after the first 80 procedures have been completed. Findings will be reviewed with the investigators, and decisions will be made as to whether or not the research study continues. These interim reviews and outcomes will be reported to the IRB.

f. Withdrawal of Subjects

Subjects will be withdrawn from the study if they experience an adverse drug reaction defined as anaphylaxis. Other potential side effects such as nausea, vomiting, or diarrhea will be treated symptomatically per standard of care. If refractory to standard treatment for these side effects, subjects will be withdrawn from the study. Subjects experiencing any thrombotic event prior to completion of study drug dosing schedule will be withdrawn from study. Subjects may choose at any time to voluntarily withdraw from the study. If subjects choose to withdraw, No further data will be collected. Data already collected will be included in the study.

The primary investigator may remove a subject at any time from this research study if it is felt to be in the best interest of the subject.

8. Statistical Plan

a. Sample Size Determination

The primary outcome variable for the study is transfusion following a procedure. The analysis will be performed using generalized estimating equations (GEEs), as each individual may have multiple surgical procedures that may be randomized to either the control or TXA treatment prior to EACH procedure. An initial assessment for sample size for a McNemar test, assuming that the transfusion rate following a control procedure is 50%, the rate following a TXA procedure is 30%, $\alpha = 0.05$ and $\beta = 0.20$, indicates that 61 subjects would be needed. The control transfusion rate is based upon previous data at Spectrum Health, while the difference of 20 percentage points is based upon our estimate of what constitutes a clinically important effect. Due to the use of GEE for the analysis, a correction factor is needed.¹⁷ From previous data from the Spectrum Health Burn Unit, we assume that there will be three procedures per patient. If we further assume that the intraclass correlation coefficient = 0.8 (postulated correlation of repeated measurements), we will be able to show a statistically significant effect with 53 subjects. With an average of 3 procedures per patient, the total procedures will be 159.

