b. **Statistical Methods**

Summary statistics will be calculated. Quantitative data will be expressed as the mean±SEM and nominal data will be expressed as a percentage. Comparisons between groups for quantitative variables will be performed using the t-test. Nominal variables will be evaluated using the χ^2 test. The relationship between TXA administration and transfusion will be determined using GEE. Significance will be assessed at $p<0.05$. Analyses will be performed using intention to treat.

9. Risks to Subjects

TXA is an FDA approved medication. The safety of TXA has been demonstrated in a meta-analysis of the off-label use of TXA in the perioperative period. A theoretical risk of thromboembolic events exists, though no significant adverse outcomes have been reported with the proposed dosing schedule. Reported side effects include nausea, vomiting, diarrhea, and dizziness. Uncommon side effects include allergic dermatitis, giddiness, and hypotension. Rare side effects include blood clots, convulsions, and visual changes.

10. Potential Benefits to Subjects

Potential benefits include decreased surgical blood loss resulting in decreased transfusion requirements. Transfusion of packed red blood cells has been associated with numerous potential adverse events. In addition, decreased overall hospital cost may occur if the study subjects experience decreased complication rates.

11. Provisions to Protect the Privacy Interests of Subjects

The study, potential risks and benefits of treatment will be discussed extensively with each potential subject preoperatively in a private space. Any questions they have will be answered accordingly. Reported data will not contain identifiable information. Patient consent and all other research related activities will take place in a private exam room.

12. Provisions to Maintain the Confidentiality of Data

Identifiable study data will be kept in a secure password-protected file or locked cabinets by the Spectrum Health OCRO. The Spectrum Health OCRO will have record of the randomization of each individual subject stored in a controlled, secure area.

13. Medical Care and Compensation for Injury

Any medical or surgical complications experienced relative to this research will be treated in accordance with current standards of care. No study funds have been set aside to compensate subjects for injury.

14. Cost to Subjects

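### Section 8b leaves the primary GEE's working correlation open and makes no use of pre-operative hemoglobin; with a correlated structure, carry-over through hemoglobin would shift the estimate modestly

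*Combined protocol and SAP*

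**What the plan says.** - Section 8a defines the outcome: "The primary outcome variable for the study is transfusion following a procedure". It chooses GEE because "each individual may have multiple surgical procedures that may be randomized to either the control or TXA treatment prior to EACH procedure".
- Section 8b gives the whole specification: "The relationship between TXA administration and transfusion will be determined using GEE". No link, working correlation, covariate, procedure-order term or previous-allocation term is stated.
- Section 7c confirms the design: "Prior to each procedure, the patient will be re-randomized to receive TXA or placebo". The schedule is fixed in advance; the allocation ratio and any blocking are not given.
- Section 7a (Study Subjects) sets the only rule on spacing: "96 hours must have elapsed since the previous procedure in which the patient was randomized to drug or placebo". Section 7c expects intervals of ten days or more in practice.
- Section 7c bases transfusion on two hemoglobin thresholds, the higher one combined with symptoms, and leaves the final decision to the surgeon. It also says "Perioperative hemoglobin level data will also be collected". Hemoglobin enters no model in section 8b.
- Section 8a uses "intraclass correlation coefficient = 0.8 (postulated correlation of repeated measurements") to correct the sample size. It does not call this value the working correlation.

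**The concern.** Independent re-randomization protects a treatment-only GEE from carry-over only when the working correlation is independence. A correlated structure also compares each procedure with the same patient's other procedures. If TXA at one operation saves blood, the patient may arrive at the next with a higher hemoglobin and a lower chance of transfusion. That later outcome then enters the contrast for the earlier procedure. The 96-hour rule sets a minimum time; it does not ensure that a hemoglobin difference has gone.

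At stake are some attenuation and loss of power in a trial planned at 80%. The choice that decides whether the shift can occur is also left open, so it could be made after the data are seen. Separately, a prognostic value that the trial already collects goes unused.

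**Working it through.** **The plan's own figure.** Section 8a starts from 61 subjects (McNemar, 50% v 30%). The GEE correction with m = 3 and correlation 0.8 is 61 x (1 + 2 x 0.8)/3 = 52.87, rounded up to 53, and 53 x 3 = 159. Both stated figures reproduce.

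**Which correlations are attainable.** For outcomes with rates 0.50 and 0.30, the joint probability is at most 0.30. The largest correlation is (0.30 - 0.50 x 0.30)/sqrt(0.50 x 0.50 x 0.30 x 0.70) = 0.15/0.229 = 0.65. A value of 0.8 therefore cannot hold between a control and a TXA outcome, and no shift is given for it here. At the lower end, 61 subjects in a two-sided McNemar test needs a discordant proportion of 0.323, so the covariance is (0.50 - 0.323)/2 = 0.0885 and the correlation 0.0885/0.229 = 0.39. The range used is 0.39 to 0.65.

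**Formula.** Let the mean outcome at procedure j be a + tau x (own allocation) + lambda x (previous allocation), with independent 1:1 allocations (assumed) and m procedures. A treatment-only exchangeable GEE with identity link converges to

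tau - lambda x rho(m - 1)/{m[1 + (m - 2)rho]}.

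Under independence (rho = 0) the limit is tau. For m = 3 the factor is 2rho/[3(1 + rho)]:
- rho = 0.39: 0.78/4.17 = 0.187
- rho = 0.65: 1.30/4.95 = 0.263

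With tau = -20 points and **assumed** carry-over lambda:

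| rho | lambda = -5 points | lambda = -10 points |
|---|---|---|
| 0.39 | shift 0.9, limit -19.1 | shift 1.9, limit -18.1 |
| 0.65 | shift 1.3, limit -18.7 | shift 2.6, limit -17.4 |

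At rho = 0.65 the factor is 0.325 for m = 2 and 0.150 for m = 6.

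**Simulation at 53 x 3** (4,000 trials per setting, identity link, robust variance, true effect -0.20):

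| Estimated rho | lambda | Exchangeable estimate | Exchangeable power | Independence power |
|---|---|---|---|---|
| about 0.38 | 0 | -0.200 | 82.6% | 73.2% |
| about 0.38 | -0.05 | -0.190 | 79.9% | 73.7% |
| about 0.38 | -0.10 | -0.181 | 76.5% | 75.0% |
| about 0.65 | 0 | -0.198 | 96.2% | 70.0% |
| about 0.65 | -0.05 | -0.187 | 93.9% | 71.9% |
| about 0.65 | -0.10 | -0.173 | 90.9% | 73.9% |

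Independence estimates stayed between -0.199 and -0.202. With neither a TXA effect nor carry-over, rejection was 5.0% to 5.8% for both structures.

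**Which terms remove the shift.** In 40,000 simulated patients with lambda = -0.10 and rho about 0.38, the risk difference was -0.201 (independence), -0.182 (exchangeable), -0.182 (exchangeable plus procedure order) and -0.200 (exchangeable plus previous allocation). A procedure-order term alone does nothing.

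**Pre-operative hemoglobin.** The pathway itself was then simulated at 53 x 3, with all inputs assumed: blood loss lowers hemoglobin, hemoglobin triggers transfusion, and part of the deficit persists. Adding pre-operative hemoglobin to the exchangeable GEE brought the standardized risk difference to within about 0.005 of the independence estimate. In one setting the values were -0.166 adjusted, -0.143 unadjusted and -0.166 under independence. Power rose from 77% to 82% without carry-over, and from 51-73% to 82-86% with it.

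**The case against.** A reader might infer that the planned GEE is biased, because an assumed correlation of 0.8 seems to imply an exchangeable structure and section 8b seems to describe a model with TXA alone. The text does not support this. The 0.8 is only a sample-size input, section 8b is silent on both structure and covariates, and under independence the shift is zero. The defect in the text is an under-specified model.

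Carry-over is also unproven. The documents give no estimate of it. The usual interval runs from ten days to several weeks, and transfusion itself restores hemoglobin, more often after placebo if TXA works. In one illustrative pathway model, a gain of 2 g/dL per transfused procedure cut the attenuation of the log odds ratio from 8-9% to 2-3%, and a gain of 3 g/dL to under 1%. In another set of 12 assumed settings with gains of 0 to 2 g/dL, carry-over kept its sign and attenuation was 1% to 16%. A reversal remains possible: with lambda = +0.05 and rho about 0.38, the exchangeable estimate moves away from the null, to -0.209. This objection stands as a limit on size and on certainty of direction.

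The remedy can be challenged too. At later procedures, pre-operative hemoglobin is itself affected by earlier allocation and transfusion, and adjustment makes the odds ratio conditional. Without carry-over, the simulated log odds ratio moved from about -0.79 to -1.14. The first part was tested, and no material bias appeared. The second part stands, and standardization answers it. Independence alone is not a free answer: at rho about 0.38 its power was 73-75%, no better than the 76.5% of the shifted exchangeable analysis.

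**Conclusion.** The point holds conditionally and is modest. If a correlated working structure is used and earlier allocation changes later transfusion risk, a treatment-only GEE misses the marginal effect by about 1 to 3 points of 20. This assumes three procedures, 1:1 independent allocation, a carry-over of 5 to 10 points, and correlations of about 0.4 to 0.65. The likely direction is toward no effect. At a correlation near 0.38, simulated power falls from 82.6% to 79.9% or 76.5%. Type I error is not inflated, because without a TXA effect there is no carry-over through saved blood.

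The documents establish neither the correlated structure nor the carry-over. The case for acting does not depend on them: the primary model should be fixed in advance, and in the simulations adjusting for pre-operative hemoglobin gained power with or without carry-over. The size of that gain depends on how prognostic hemoglobin proves to be. This is a change that should be made, not a flaw that invalidates the analysis.

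**What to change.** In section 8b:
1. Name the working correlation of the primary GEE and state that the variance is robust.
2. Add hemoglobin measured before each procedure's study dose as a covariate in the primary GEE, and define which value is used.
3. Report a standardized risk difference beside the adjusted odds ratio, so that the result matches the planning comparison of 50% v 30%.
4. Pre-specify one sensitivity analysis: an independence working correlation with robust errors, or the previous study allocation plus a first-procedure indicator added to the model.

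The cost is a few sentences of analysis text, using hemoglobin data that the trial already collects. The adjusted odds ratio is conditional and needs the standardization step. The previous-allocation term costs about 2 to 3 points of power when there is no carry-over (in a separate logistic simulation, 85% v 82% at correlation 0.4 and 96% v 94% at about 0.65), but only in the sensitivity analysis.
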